3.1 Specific Objectives

1. To perform a systematic review and meta-analysis on evidence-based TB drug adherence.

2. To determine the association between the pharmacist-led intervention and medication adherence level among TB and HIV co-infected patients.
3. To assess the effects of different levels of adherence with therapeutic impact and its possible clinical outcomes.
4. To assess the survival trend with the study population and health-related quality of life (HRQoL) by using the EQ5Dv3 tool.
5. To assess the defaulter patients' approach towards TB and its treatment outcomes.
(Qualitative Approach)

4. Ethical Approval

The study protocols will be approved by the Ethical and Research Committee Ministry of Health, Malaysia. The protocol will also be registered at clinicaltrials.gov

5. Methodology

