The study will be ended after 6th month, but still, if the patients are non-adherent to the therapy the study period will be extended to 1 year.

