5.8 Data Analysis

All analyses were performed using SPSS software, version 28.0 (SPSS Inc., Chicago, IL, USA). *T-test*, $\cong \chi^2$ test, Fisher's exact test, and a logistic regression model were used to determine differences between the intervention group and the control group. According to log-likelihood values, the best fit for the correlation structure was determined to be a compound symmetry structure and random effects were applied to the slope as well as to the intercept. In addition, analysis of variance (ANOVA) was used to determine differences between the two groups based on each monthly accumulated drug adherence rate. Statistical significance was set at $p < 0.05$ (16)

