Subjects can choose to withdraw at any time. Subjects may be withdrawn if the investigator deems that it is detrimental or risky for the subject to continue. As this is a prospective observational study and data in the form of information are only required, the literature suggests about 10-20% dropout or withdrawal has been observed in the past so 20% dropout is already included in the sample size calculation thus the withdrawn subjects will not be replaced with new subjects.

10. Selection of subjects to be included in the analysis

All the subjects who will participate until the end of this study will be included in the final analysis of this study. All subjects who withdraw from the study at any point in time will not be included in the final results analysis.

11. Risk-Benefit Assessment

As stated above, there is no risk from the investigational process and study procedures. No harm could be caused to the patient as there is no invasive procedure involved in the study nor any

Medication is given to the patient. Only non-clinical intervention is given in the study. Study findings shall potentially improve treatment outcomes. The expected benefit outweighs the minimal risk to subjects and thus this study should be supported.

If still any injuries do occur as a direct result of participating in the study, treatment for such injuries shall be provided or paid for by the researcher/ sponsor.

12. Ethics of Study

The study will be conducted in compliance with ethical principles outlined in the Declaration of Helsinki and the Malaysian Good Clinical Practice Guideline.

All aspects of the study protocol, including access to and the use of clinical information of patients, and demographics will get approval by the institutional medical ethics committee locally as well as central health authorities before initiation of this study. Information on individuals will be strictly protected and used for clinical research only.

13. Informed Consent/Assent Process

Patients shall be informed of the study during their usual clinic visits. They will be requested to contact investigators if they are interested. An appointment will be made where the patient information sheet will be provided and explained to them. If they are willing to participate, the consent forms will be signed and dated. If they need to, they are allowed to take the information sheet home to consult with their family members, and another day for getting consent arranged.

14. Conflict of Interest

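### Objective 4 asks for a survival trend, but section 5.8 names no time-to-event method and the completer rule in section 10 distorts the estimate on either reading

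*Combined protocol and SAP*

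**What the plan says.** - **Objective (section 3.1, item 4).** "To assess the survival trend with the study population and health-related quality of life (HRQoL) by using the EQ5Dv3 tool". The plan does not define the survival trend: it gives no event, time origin or censoring rule.
- **Methods (section 5.8).** A t-test, chi-square test, Fisher's exact test and "a logistic regression model were used to determine differences between the intervention group and the control group". There is also a longitudinal model in which "random effects were applied to the slope as well as to the intercept", with no outcome named, and an ANOVA "to determine differences between the two groups based on each monthly accumulated drug adherence rate". No survival method appears.
- **Analysis set (section 10).** "All the subjects who will participate until the end of this study will be included in the final analysis of this study". Also: "All subjects who withdraw from the study at any point in time will not be included in the final results analysis". Death is not mentioned.
- **Length of follow-up (section 5.5).** Six months, but "if the patients are non-adherent to the therapy the study period will be extended to 1 year". Section 5.2 places the study between November 2022 and November 2023.
- **Allocation (sections 5.1, 5.4 and 6).** Random, 1:1, with 420 patients planned.

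**The concern.** A survival trend is the proportion still alive as time passes. To estimate it, every patient must count from a common origin until death or until last known to be alive. Section 10 instead selects patients by what happened to them later. Depending on how a death is classed, the rule removes either the events themselves or the time that withdrawn patients spent alive under observation. Adding Kaplan-Meier to section 5.8 would not cure this while section 10 stands.

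A second problem arises if deaths are counted: the observation period depends on adherence. The study's overall aim is to relate adherence to clinical outcomes, so a crude death proportion by adherence level is a natural table to produce, and it would compare groups with different time at risk.

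**Working it through.** **What there is to reproduce.** The documents give no mortality rate, hazard ratio or number of deaths. The mortality and withdrawal figures below are therefore assumptions, except the 20% dropout, which is in sections 6 and 9. I take 420 randomised patients as printed. (That figure does not follow from 382 with 20% attrition, since 382/0.8 = 477.5, or 478. This is a separate matter and nothing here depends on it.)

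**Reading A: a patient who dies has not stayed to the end.** Every death before month 6 leaves the analysis set. Survival is n/n = 100% in each arm, whatever the true mortality.

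**Reading B: deaths are kept and withdrawals are dropped.** Let m be true 6-month mortality and w the 6-month withdrawal probability, with constant hazards and withdrawal unrelated to death.

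- λ = −ln(1−m) and ω = −ln(1−w), per 6 months
- Alive and still in at month 6: S = (1−m)(1−w)
- Deaths seen: D = [λ/(λ+ω)] × (1−S)
- Mortality as section 10 would report it: D/(D+S)

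For m = 10% and w = 20%: λ = 0.1054, ω = 0.2231, S = 0.720, D = 0.3207 × 0.280 = 0.0898. Reported mortality = 0.0898/0.8098 = 11.1%.

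| True 6-month mortality (assumed) | Reported, 20% withdrawal |
|---|---|
| 5% | 5.6% |
| 10% | 11.1% |
| 15% | 16.5% |
| 20% | 22.0% |

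With equal true mortality of 15% but different withdrawal by arm:

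- w = 10%: S = 0.765, D = 0.1426, reported 0.1426/0.9076 = 15.7%
- w = 30%: S = 0.595, D = 0.1268, reported 0.1268/0.7218 = 17.6%

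The arms differ by 1.9 percentage points although true mortality is the same.

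**Does the proposed analysis remove the bias?** Take the m = 10%, w = 20% case and count withdrawn patients' time. Observed time per patient is (1−S)/(λ+ω) = 0.280/0.3285 = 0.852 six-month units. Deaths per unit are 0.0898/0.852 = 0.1054 = λ, so survival is exp(−0.1054) = 90%. The true value is recovered.

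**Unequal follow-up (only where deaths are counted).** At constant hazard, 10% at 6 months becomes 1 − 0.9² = 19% at 12 months. That is the ceiling. At 9 months of observation it is 1 − 0.9^1.5 = 14.6%.

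**Would an arm comparison be informative?** Assume control 6-month mortality of 5% to 20%, hazard ratios of 0.5 to 0.8, 210 per arm and 20% withdrawal, censored. About 14 to 69 deaths are expected. Deaths needed for 80% power at two-sided 0.05 are 4 × (1.960 + 0.842)²/(ln HR)²:

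| Hazard ratio | Deaths needed | Deaths expected | Power |
|---|---|---|---|
| 0.5 | 66 | 14–58 | 26–75% |
| 0.6 | 121 | 15–61 | 17–52% |
| 0.7 | 247 | 16–65 | 11–30% |
| 0.8 | 631 | 17–69 | 7–15% |

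**The case against.** **Death need not count as withdrawal.** Section 9 describes withdrawal as the subject's choice or the investigator's decision, and the explicit exclusion in section 10 covers those who withdraw. On that view reading A fails and only the modest distortion of reading B remains. This stands as far as it goes: the 100% figure is conditional. But section 10's inclusion sentence requires staying to the end, nothing exempts deaths, and reading B is still biased.

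**The listed tests can handle mortality.** Logistic regression, chi-square or Fisher's exact test can estimate or compare 6-month mortality if vital status is known for every randomised patient. This stands, so it would be wrong to infer that the tests alone are at fault. The difficulty is their combination with section 10. Even with full vital status they would give one time point, not a trend.

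**The objective is descriptive.** Objective 4 refers to the study population and names no comparison of arms. This stands. A Kaplan-Meier curve with confidence intervals answers it; log-rank and Cox analyses go further than the objective requires.

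**The doubling of exposure is a ceiling.** If the November 2022 to November 2023 window includes follow-up, only patients enrolled at its very start could reach 12 months. If non-adherence is judged at month 6, only patients alive then can be extended. Both points stand.

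**The study is observational.** Section 9 says so, but sections 5.1, 5.4 and 6 describe a randomised superiority trial. A purely descriptive cohort curve would still need all enrolled patients and a censoring rule.

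**Conclusion.** The point holds. As written, sections 5.8 and 10 do not give a valid answer to the survival part of objective 4. The size depends on a choice the plan leaves open: 100% survival by construction if a death is a non-completion; otherwise overstated mortality, by about 0.6 to 2.0 percentage points for assumed true mortality of 5% to 20% with 20% withdrawal, plus a false arm difference if withdrawal is unequal. These figures assume constant hazards and withdrawal unrelated to death.

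A reader might infer two stronger claims. One is that the plan yields both 100% survival and nearly doubled deaths in non-adherent patients. These need opposite readings of section 10 and cannot both occur. The other is that the extended follow-up doubles exposure between the trial arms. Section 5.5 ties the extension to adherence, so the ratio of up to 12/6 applies between adherence groups, not between arms.

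**What to change.** 1. **Section 10.** For objective 4, replace the completer rule with all randomised patients, and state that deaths are events, not withdrawals.
2. **Section 5.8.** Define the outcome as all-cause survival from randomisation, estimated by Kaplan-Meier with confidence intervals. Censor withdrawals at last contact and everyone still alive at a common month-6 cut-off. The cut-off removes the unequal observation time without altering the extension in section 5.5.
3. **Arm comparison.** If log-rank or Cox results are given, label them secondary and report the hazard ratio with its interval. Section 6 contains no mortality rate or hazard ratio, so the trial is not sized for this comparison.
4. **Survival by adherence level, if reported.** Adherence is measured after baseline, so use a landmark or time-dependent analysis.

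**Cost.** Items 1 to 4 are wording. The real cost is data: section 5.4 uses the attendance book only to confirm refill visits, and no section plans to record deaths. Date of death or last contact must be added as a data item, with vital status after withdrawal where consent allows. Without the latter, deaths soon after withdrawal would be missed and censoring at last contact could understate mortality.

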5.1 Study Design

A longitudinal study design will be adopted to achieve the present study objectives. The study population will be classified with one intervention and one control arm, using a 1:1 allocation ratio, to evaluate whether the intervention is superior to the control treatment will be adopted to achieve the study objectives at General Hospital Penang.

Intervention arm: Enrolled participants will be counseled and educated by a pharmacist on the therapy and benefits of adherence.

Control arm: Enrolled patient will be counseled and educated by the material provided on the therapy and benefits of adherence.

5.2 Study Setting

The study will be conducted at Hospital Pulau, Penang from November 2022 to November 2023. We will enroll patients with culture-confirmed TB. Additionally, the enrolled PLHIV with any TB symptoms will be investigated with sputum smear microscopy, mycobacterial culture (BACTEC MGIT), Xpert Ultra, and Chest X-ray (CXR). Patients will be eligible for enrolment if they are ≥ 18 years of age, diagnosed with active TB according to national TB program guidelines, had not been previously treated for these diseases, agreed to start treatment for TB, and could give informed consent in either English or Malay.

In Malaysia, a DOT program has been implemented in two phases, “intensive” and “continuation”. In the intensive phase (daily DOT) the current standard anti-TB regimen recommended by WHO

Consists of a 2-month treatment with INH, rifampicin (RIF), pyrazinamide (PZA), and ethambutol(EMB), followed by a 4-month continuation phase with INH and RIF (2EHRZ/4HR) as daily regimen. In the intensive phase (daily DOT), a patient takes their medication in front of the healthcare worker every day at a health facility. In the continuation phase (non-daily DOT), a patient is given the responsibility to take the medication at home and come to a health facility weekly for health checking and medication refilling.

5.3. Participants

Adult TB and HIV co-infected patients who are receiving treatment at specific public health facilities in Penang, Malaysia will be prospective participants for the study.

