5.4. Data Collection and Management

A trained healthcare professional team will collect and supervise the data collection. Enrolled participants will answer a brief questionnaire focused on recent isoniazid adherence. Patients will be asked to report their recent adherence, including the date of their most recent dose. They will be also asked to estimate how many of the last thirty doses they had missed or how many doses they missed in a typical week and the reasons for any missed doses. Data will be collected from the primary source through interviews and sample urine collection, and a secondary source by a review of the health facility attendance registration book to confirm the patient's medication refill visit attendance. A trained pharmacist and nurses will collect urine specimens in a clean and dry container. Urine collected at any time of the day may be used. The sample does not have to be freshly voided as the sample can be stored at room temperature for 1 to 10 days and thereafter at -20°C and retain its suitability for testing. The urine sample will be collected on day 0, and then after every 2 months i.e., 2 months, 4 months, and 6 months. The urine sample will be discarded immediately after the analysis. A health worker will be trained to administer the EQ-5D. Enrolled patients will be explained the purpose and duration of the study. All participants included in the study provided informed consent and completed the EQ-5D facilitated by the trained health worker in a face-to-face interview at the clinic. The interview will be conducted on the premises of the hospital. Interviews will be conducted at the start of the study, after 2 2-month visits, and then at the end of the study (6th month). To ensure the security of the patients' information, a double-blind randomization technique will be adopted. The computer gives each patient a code number, and the code numbers will then be allocated randomly to the treatment groups. All data will be kept in a database, and backup file with password protectors. All identifiable information will be removed

And replaced by code. Code breaking will be done by the external personnel who are not involved in the study so the biasedness couldn't be possible. At the end of the trial, the patients can check their records on request. The study record shall be destroyed after the research is completed.

5.5. Study End Point:

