5.6. Inclusion Criteria

Patients have to meet the following criteria,

- Men and women aged 18 years or more.
- Newly bacteriologically confirmed TB case (less than a month since diagnosis). This restriction (not more than one month of treatment) does not refer to patients whose most recent treatment outcome was a failure and who were assigned to a new treatment regimen.
- No plans to move out of the clinical settings of the participating TB program sites within 9 months of enrollment.

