5.11 Specimen Storage for Future Use

Urine analysis will be discarded immediately after the analysis. No sample will be reused in any further research.

6. Sample Size

The sample size for the current study is based on a statistical superiority trial (continuous data) design of a randomized control trial. Based on the nature of the relevant amount, a superiority design contains statistical superiority trials and clinical superiority trials (9).

$$N = \frac{2 \times Z_{1-\alpha/2}^2 \times (p_0(1-p_0) + p_1(1-p_1))}{d^2} \times S^2$$

Where N is the size per group, p_0 is the response rate of the standard treatment group; p_1 is the response rate of the treatment group; z is the standard normal deviate for a 1 or 2-sided α ; d is the real difference between 2 treatment effect; α a clinically acceptable margin; and S is the Pooled standard deviation of both comparison groups. By following this design and keeping in mind the prevalence of TB

And HIV co-infection in Malaysia, i.e., is 5.9%, the calculated sample size calculated is 382 individuals (191 subjects per arm). We'd need a minimum final sample size of 420 people if we assume a 20% attrition rate (210 per group). All estimates are based on a two-sided test with a significance level of $p < 0.05$.

7. Privacy and Confidentiality

Subject's names will be kept on a password-protected database and will be linked only with a study identification number for this research. The identification number instead of patient identifiers will be used on subject data sheets. All data will be entered into a computer that is password-protected. On completion of the study, data in the computer will be copied to CDs, and the data in the computer erased. CDs and any hardcopy data will be stored in a locked office of the investigators and maintained for a minimum of three years after the completion of the study. The CDs and data will be destroyed after that period of storage. Subjects will not be allowed to view their study data, as the data will be consolidated into a database. Subjects can write to the investigators to request access to study findings.

8. Termination of Study

The researcher/ sponsor may decide to terminate the study at any time. Subjects will be informed if the study is terminated and follow-up visits will be arranged if needed. The criteria for termination depend on unseen circumstances and, the incorporation of the patients.

9. Withdrawal Criteria

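### The protocol does not settle whether one hospital or several facilities take part; if several, allocating and analysing without facility gives up a little precision

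*Combined protocol and SAP*

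**What the plan says.** **Number of sites.** Section 5.1 says that the design "will be adopted to achieve the study objectives at General Hospital Penang". Section 5.2 places the study at a single hospital too, under a different name (Hospital Pulau, Penang), and section 5.4 holds the interviews on the premises of the hospital, in the singular. Section 5.3, by contrast, draws participants from among adults "receiving treatment at specific public health facilities in Penang, Malaysia", and section 5.6 requires "No plans to move out of the clinical settings of the participating TB program sites within 9 months of enrollment".

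**Where adherence is produced and recorded.** Section 5.2 locates daily observed dosing and weekly refill visits at a health facility. Section 5.4 uses that facility's attendance register as a secondary adherence source.

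**Allocation and analysis.** Section 5.1 gives a 1:1 ratio. Section 5.4 says that the computer issues each patient a code and that "the code numbers will then be allocated randomly to the treatment groups". It mentions no blocks, strata or site lists. Section 5.8 lists a t-test, chi-square and Fisher's exact tests, logistic regression and ANOVA to compare the arms. It also mentions random effects on intercept and slope without naming the unit they belong to. No facility term appears.

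**The concern.** Dosing, refills and part of the adherence record all sit at facility level. If several facilities take part and differ in how they observe, refill or keep registers, facility will explain some of the variation in recorded adherence. It is known before allocation, so that variation can be removed at almost no cost.

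Unrestricted allocation leaves each facility's share of the two arms to chance. An analysis without facility then leaves the between-facility variation in the error term. At stake is a wider standard error than necessary. The contradiction about sites also has a consequence of its own: a reader cannot tell what population is sampled or whether facility needs to be handled at all.

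**Working it through.** The plan gives no figure on this point, so there is none to reproduce. The check asks how much precision is lost if there is more than one facility.

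**Inputs from the plan (sections 5.1 and 6)**
- 1:1 allocation and 191 per arm before attrition, taken as given. It cannot be recomputed, because the response rates, the difference ("d is the real difference between 2 treatment effect") and the standard deviation ("S is the Pooled standard deviation of both comparison groups") have no values.
- Two-sided 5% level: "All estimates are based on a two-sided test with a significance level of" p < 0.05.

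**Assumptions, because the plan gives no values**
- Power of 80% without adjustment. The printed formula has no power term.
- Two or four facilities.
- A share ρ of outcome variance between facilities, from 1% to 10%.

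**Step 1: chance imbalance.** Take two facilities of 191 patients each, with arms fixed at 191:191 and no strata. The number from one facility in one arm is hypergeometric:
- Variance = 191 × 0.5 × 0.5 × 191/381 = 23.9, so SD = 4.89.
- SD of the difference in that facility's share between arms = 2 × 4.89/191 = 5.1 percentage points.
- 95% range for one facility's split: about 86:105 to 105:86.

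Simulation (200,000 runs) gives the chance that a facility's share differs between arms by 10 points or more: 4.1% for two equal facilities, 1.4% for an 80/20 split, and 8.9% for any one of four equal facilities.

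**Step 2: what an imbalance does to the arm difference.** Assume adherence of 70% and 90% at two equal facilities, a gap of 20 points:
- Between-facility share of variance = 0.10²/(0.80 × 0.20) = 6.25%.
- Typical shift in the arm difference = 5.1 points × 0.20 = about 1.0 point.
- Shift at a 10-point imbalance = 10 × 0.20 = 2.0 points.

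Other assumed gaps give these shares:
- 80% v 90%: 0.05²/(0.85 × 0.15) = 2.0%.
- 85% v 90%: 0.025²/(0.875 × 0.125) = 0.6%.

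**Step 3: power.** The standardised effect that gives 80% power at 191 per arm is (1.960 + 0.8416) × √(2/191) = 0.287 SD. Stratifying and adjusting reduces the residual SD to √(1 − ρ), so

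power = Φ(2.8016/√(1 − ρ) − 1.960), and n per arm for 80% power = 191 × (1 − ρ), rounded up.

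| ρ | Power | n per arm for 80% |
|---|---|---|
| 0 | 80.0% | 191 |
| 0.01 | 80.4% | 190 |
| 0.02 | 80.8% | 188 |
| 0.05 | 82.0% | 182 |
| 0.10 | 84.0% | 172 |

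The gain is 0.4 to 4 points of power. It requires facility in the analysis model; stratified allocation alone does not deliver it.

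**The case against.** **There may be only one site.** The operational statements in sections 5.1, 5.2 and 5.4 favour a single hospital, and the health facility in section 5.2 appears in a description of the national programme, not in a list of study sites. This stands: the statistical part of the point is conditional. It does not dispose of the plural wording in sections 5.3 and 5.6. Several facilities is also a realistic reading. If all follow-up must fit inside the 12-month study period, a 6-month follow-up leaves about 6 months to enrol 420 patients, or 420/6 = 70 a month.

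**Silence is not a decision.** The plan does not reject stratification. It gives one short account of allocation, and section 5.8 names no covariates of any kind. This also stands, and the point should be read as an improvement to what is stated.

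**Nothing shows that practice differs by facility.** True: section 5.2 describes one national programme, so ρ is purely an assumption. One might take the two ends of the 8% to 33% non-adherence range in section 5.10 as two facilities. That gives 0.125²/(0.795 × 0.205) = 9.6% of variance. But the range comes from published studies, not from facilities in Penang, so it marks only the extreme end. Even there, the standard error of the arm difference falls only from 4.1 to 3.9 points.

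**A stronger reading that fails.** A reader might infer that one facility's practice could pass for a counselling effect. Under random allocation, chance imbalance is already reflected in the unadjusted standard error and the type I error is preserved, so the documents do not support a claim of bias.

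**Conclusion.** The contradiction is real and needs correcting whatever the number of sites: sections 5.1, 5.2 and 5.4 point to one hospital, sections 5.3 and 5.6 to several facilities or sites.

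The statistical consequence is minor and conditional. With more than one facility, the stated allocation and analysis give up about 0.4 to 4 points of power, on the assumptions of 191 analysed per arm, 80% unadjusted power, a comparison of means, and 1% to 10% of outcome variance between facilities. With one facility the loss is zero. Validity is not in question.

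A reader might also want results broken down by counselling pharmacist. The documents do not support that as a comparison between arms: under section 5.1 control patients are educated from provided material and have no specified counselling pharmacist.

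**What to change.** 1. Make sections 5.1, 5.2, 5.3, 5.4 and 5.6 agree, with a named list of the participating facilities. Say whether the two hospital names in sections 5.1 and 5.2 refer to the same place.
2. If there is more than one facility, amend section 5.4 so that the computer allocates 1:1 in randomly varying permuted blocks within facility. Define facility, before allocation, as the site where the patient receives observed dosing and refills. If one hospital enrols and others dispense, stratifying by enrolling site would achieve nothing.
3. In section 5.8, include facility in the arm comparisons: a linear model with a facility term in place of the t-test, a facility-stratified test in place of the plain chi-square, and a facility term in the logistic regression.
4. Record each patient's facility on the data form.

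The cost is a revised randomisation list, one form field and one model term. The list is easiest to change before enrolment. The one downside is that very small facilities must be pooled into a single stratum, by a rule fixed in advance. If there is only one facility, step 1 is all that is needed.
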